8.3.6 SERIOUS ADVERSE EVENT REPORTING

In consultation with the PI, a trained member of the study team will be responsible for conducting an evaluation of a serious adverse event. Adverse events meeting the guidelines for required reporting to

the IRB will be reported according to UW IRB reporting guidelines (see <https://irb.wisc.edu/manual/investigator-manual/post-approval-responsibilities/reportable-events/?tab=reporting-requirements>). A copy of IRB-reportable events will be sent the ICTR DMC Protocol Review Manager within the same time frame as required for reporting to the IRB. A report compiling all adverse events will be reviewed by the DMC on an annual basis.

All serious adverse events will also be reported to the NICHD according to their policy. See <https://www.nichd.nih.gov/grants-contracts/process-strategies/policies/data-safety>.

8.3.7 REPORTING EVENTS TO PARTICIPANTS

N/A

8.3.8 EVENTS OF SPECIAL INTEREST

1. Detection of previously undisclosed dangerous or potentially dangerous situations or occurrences. It is possible that families may disclose information to our research staff that indicates they have been or may be subject to dangerous situations. Situations or occurrences that might be disclosed to or observed by the research staff and would require the staff to complete an incident report include but are not limited to child abuse, imminent threat to self, and imminent threat to others (even though our questionnaires will not specifically ask about these issues). General procedures we will take in these situations are outlined below. Specifically, any suspected child abuse must immediately be reported to the Wisconsin Department of Child Protective Services (CPS) or Los Angeles Department of Child and Family Services (DCFS) and, if any immediate danger is possible to the child, family or other individual, to the local Police Department. The social worker on call will be notified immediately if a participant discloses suicidal ideation or domestic violence. In any adverse situation possibly related to the research study, [name], [name], and the IRB will also be notified.
2. Accidental disclosure of confidential material. It is possible that despite careful procedures to protect private information, there could be accidental disclosure of confidential information. To protect against accidental disclosure, we will only use ID numbers on questionnaires and will keep any links to personal identifying information on REDCap. In the case of any breach of confidentiality we will notify the participant, PI and site-PI, and the IRB.
3. Distress experienced during or after completing research survey. It is unlikely for parents to experience distress in typical clinical encounters or when given the survey questions, and if any distress does occur it would most likely be mild and transient. However, we are attentive to the possibility that answering personal questions may be upsetting for some individuals. To protect against this distress, participants will be made aware that participation in the research study is entirely optional, has no effect on their children's medical care, that they may choose not to answer certain questions and that they may end their participation at any time. If a participant expresses distress, the research assistant will immediately notify PI / site-PI. Participants will also be given phone numbers (in the informed consent process) to contact the study PI and the IRB in case of distress during or after the study interview. In addition, on-call social workers at our clinics will be notified to help with any distress that may arise.

8.4 UNANTICIPATED PROBLEMS

8.4.1 DEFINITION OF UNANTICIPATED PROBLEMS

This protocol uses the definition of Unanticipated Problems as defined by the Office for Human Research Protections (OHRP). OHRP considers unanticipated problems involving risks to participants or others to include, in general, any incident, experience, or outcome that meets all of the following criteria:

- Unexpected in terms of nature, severity, or frequency given (a) the research procedures that are described in the protocol-related documents, such as the Institutional Review Board (IRB)-approved research protocol and informed consent document; and (b) the characteristics of the participant population being studied;
- Related or possibly related to participation in the research ("possibly related" means there is a reasonable possibility that the incident, experience, or outcome may have been caused by the procedures involved in the research); and
- Suggests that the research places participants or others at a greater risk of harm (including physical, psychological, economic, or social harm) than was previously known or recognized.

8.4.2 UNANTICIPATED PROBLEMS REPORTING

The investigator will report unanticipated problems (UPs) to the reviewing IRB following reporting guidelines (see <https://irb.wisc.edu/manual/investigator-manual/post-approval-responsibilities/reportable-events/?tab=reporting-requirements>). A copy of such reports will be sent to the Data Coordinating Center (DCC).

The UP report will include the following information:

- Protocol identifying information: protocol title and number, PI's name, and the IRB project number
- A detailed description of the event, incident, experience, or outcome
- An explanation of the basis for determining that the event, incident, experience, or outcome represents an UP
- A description of any changes to the protocol or other corrective actions that have been taken or are proposed in response to the UP

9 Statistical Considerations

9.1 STATISTICAL HYPOTHESES

- Primary Feasibility, Acceptability, Fidelity Endpoint(s): RE-PACT's primary outcomes will be analyzed descriptively, and evaluate feasibility, acceptability, fidelity using multiple approaches. Each outcome will be

assessed against our pre-specified measures of success, e.g., achieving at least 80% enrollment. By conducting iterative refinements over three waves of implementation, we expect to achieve success in all measures. We will assess all participant feedback using both quantitative and qualitative data to determine what study design changes would enhance a large-scale RCT. We will use inductive content analysis of qualitative data.

- Secondary Efficacy Endpoint(s): **To inform a future large multisite RCT, we will test** differences between treatment (I or AC) groups in the primary and secondary respiratory illness outcomes. Our goal with these analyses is to estimate effect sizes for the differences between groups. The primary clinical outcome is severe respiratory illness rate, defined as the total number of severe respiratory illnesses divided by the person-months over the 6 months period. The severe respiratory illness rate will be analyzed with negative binomial (NB) regression models to account for overdispersion in the count data. In the primary analysis, univariate NB regression analysis will be conducted with study arm as a predictor variable. Study site will be a stratification factor to account for stratified randomization. The observed effect size of the analysis will be quantified in terms of relative risk (RR) and reported along with the corresponding 95% confidence interval. A generalized linear mixed effects model with a logit link function and subject specific random effects will evaluate **longitudinal changes** in the severe respiratory illnesses within and between study arms. An autoregressive (AR) correlation structure will account for within subject correlations. In this analysis, presence/absence of severe respiratory illness at the monthly assessments will be the dependent variable; study arm will be included as a predictor variable, and study site as a stratification variable to account for the stratified randomization. **To investigate theoretical mechanisms**, we will test the mediating effect of caregiver capability, opportunity, and motivation (COM-B)¹¹³ measures on the relationship between intervention and respiratory exacerbations.

9.2 SAMPLE SIZE DETERMINATION

We will enroll a total of 90 participants. Wave 1 will contain 10 participants (5 UW, 5 UCLA); Wave 2 will contain 20 participants (10 UW, 10 UCLA); Wave 3 will contain 60 participants (30 UW, 30 UCLA). Based on this team's preliminary work, eligible children average one severe respiratory illness per year and we estimate 50% of participants will experience at least one respiratory illness during the period of enrollment. We expect to be able to maintain contact and collect data from ≥90% of the participants at the final follow-up, evenly divided between intervention and control groups. We assume this sample will not be powered to establish the efficacy of the intervention; however, it will provide a sufficient sample to determine feasibility and estimate effect sizes which will be used for power calculations in the future large RCT. The following table shows the attainable power levels for detecting various differences in severe respiratory illness rates (primary clinical outcome) between study arms at the two-sided 0.05 significance level, based on a NB regression model with an overdispersion parameter of $\phi=1.0$.

Attainable power levels for detecting differences in severe respiratory illness rates between arms at the two-sided 0.05 significance level based on a NB regression model, assuming a sample size of 45 subjects per arm with a missing value rate of 10% or less.

Relative Risk (RR)	Number of severe respiratory illnesses in intervention arm over 6-month Follow-up period				
	5	10	15	20	25

(Control vs. Intervention) ($\lambda=0.02$)*	($\lambda=0.40$)*	($\lambda=0.06$)*	($\lambda=0.08$)*	($\lambda=0.10$)*
3.0	19%	29%	38%	45%
4.0	31%	41%	59%	68%
5.0	42%	62%	74%	83%

*Severe respiratory illness rate per patient-month

Hence, large effect sizes with RRs ranging between 3.0-5.0 for comparing the severe respiratory illness rates between study arms will be detected with 19-88% power at the two-sided 0.05 significance level.

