Preventing Respiratory Illness in Severe CP Requires Broad, Adaptive, Timely Intervention. Action planning and health coaching are effective strategies in other populations. For example, from 2003 to 2013, hospitalization rates for pediatric asthma dropped by half (from 9.6% to 4.7%), during which time asthma action plan use increased significantly.⁴² A family intervention linking home-based asthma coaching to action planning significantly reduced hospitalizations in poorly controlled asthma.⁴³ However, respiratory illness in severe CP has broad comorbid triggers, e.g., emesis, dysphagia, aspiration, seizures, among others. Simple action plans or coaching alone cannot address the breadth of respiratory illness triggers or potential responses. For example, if a parent of a child with severe CP follows an action plan directed towards bronchospasm, it would not effectively address an acute infectious lower respiratory infection. Parents of children with severe CP need action plans and coaching, but they also need an efficient direct extension to their clinical team for adaptive, just-in-time clinical response directed specifically to real-time acute problems.

The Plans for Action and Care Transitions (PACT) intervention was developed by this team to prevent hospitalizations for children with complex chronic diseases including severe CP. After integrating systematic literature review,⁴⁴ parent interviews,³⁸ and a national expert panel,³⁹ each focused on preventing hospitalization, PACT was designed to leverage evidence-based strategies from different populations: asthma action planning,⁴⁵⁻⁴⁷ health coaching,⁴⁸⁻⁵⁰ and feedback at our Parent Advisory Group's monthly meetings. PACT delivered action planning and coaching activities to children with diverse complex diseases, including severe CP, and a PACT RCT found 40% lower hospitalization rates for intervention vs control patients.¹⁸

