6.3 MEASURES TO MINIMIZE BIAS: RANDOMIZATION AND BLINDING

Random allocation will be concealed to research staff conducting recruitment and will use a 1:1 allocation with random block sizes of 2 and 4. Block randomization will be achieved with a computer-generated random number list prepared by the study biostatistician having no clinical involvement in the trial. Randomization will be stratified by site (UW vs UCLA) to account for site-specific study characteristics. After the research team member obtains participant consent, they will telephone contact the study project manager who is independent from the recruitment process to receive the group assignment. Alternatively, it may be arranged that randomization will be built into the REDCap database by the study biostatistician.

Since this study aim is feasibility, acceptability and fidelity, there is no plan for whether/when to break randomization codes. Study and clinical team members cannot practically be blinded to treatment because only those randomized to intervention will receive text messages, specific action plans, and coaching. The need for clinical team members to create action plans and interact with coaches will identify those randomized to intervention. Presumably, the need for admission to the hospital for a respiratory illness and secondary clinical endpoints (ED visits, need for antibiotics, steroids, hospital days, and death) are less prone to observer bias. The outcome evaluator (study biostatistician) will remain blinded during analyses.

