9.4.3 ANALYSIS OF THE SECONDARY ENDPOINT(S)

Clinical Outcomes. We will test differences between treatment (intervention or control) groups in the primary and secondary respiratory illness outcomes. Our goal with these analyses is to estimate effect sizes for the differences between groups which will allow precise sample size calculations for a future large-scale trial.

Primary clinical outcome is the severe respiratory illness rate, defined as the total number of severe respiratory illnesses divided by the person-months over the 6-month follow-up period. The severe respiratory illness rate will be analyzed using a negative binomial (NB) regression model to account for overdispersion in the count data. For the primary analysis, univariate NB regression analysis will be conducted with study arm as a predictor variable. Study site will be included as a stratification factor in the primary analysis to account for stratified randomization. The observed effect size of the analysis will be quantified in terms of relative risk (RR) and reported along with the corresponding 95% confidence interval.

As a secondary analysis, multivariate NB regression analysis will be performed to compare the severe respiratory illness rates between study arms. In this analysis, clinical and demographic characteristics will be included as covariates in an initial non-parsimonious model. The least absolute shrinkage and selection operator (lasso) and elastic net penalty methods for negative binomial regression models will be utilized to identify a parsimonious model with independent covariates. These methods are considered state-of-the art techniques for variable selection (Wang Z., et al. Stat Methods Med Res. 2016).

Longitudinal changes in the severe respiratory illnesses within and between study arms, will be evaluated with generalized linear mixed effects model with a logit link function and subject specific random effects. An autoregressive (AR) correlation structure will be utilized to account for within subject correlations. In this analysis, the presence/absence of severe respiratory illness at the monthly assessments will be the dependent variable, study arm will be included as a predictor variable and study site as a stratification variable to account for the stratified randomization.

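### The power table in Section 9.2 disagrees with its own paragraph: 12 of 15 cells need control rates well above the stated one illness per year, and the printed powers match one month of exposure, not six

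*Combined protocol and SAP*

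**What the plan says.** Section 9.2 states that "eligible children average one severe respiratory illness per year" and, separately, estimates that half of participants will have at least one respiratory illness while enrolled. It then tabulates power from a negative binomial model with overdispersion 1.0 at two-sided 0.05, "assuming a sample size of 45 subjects per arm with a missing value rate of 10% or less".

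The columns are 5, 10, 15, 20 and 25 severe illnesses in the intervention arm over six months, with rates per patient-month of 0.02 to 0.10 (the second is printed as 0.40). The rows are relative risks, control versus intervention, of 3, 4 and 5. The closing sentence is that "large effect sizes with RRs ranging between 3.0-5.0 for comparing the severe respiratory illness rates between study arms will be detected with 19-88% power".

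Section 9.4.3 gives the outcome as a rate, "defined as the total number of severe respiratory illnesses divided by the person-months over the 6-month follow-up period". Section 2.2 reports that the earlier PACT trial "found 40% lower hospitalization rates for intervention vs control patients". Section 2.1 makes clear that this was all-cause hospitalization in children with a mix of complex diseases.

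Sections 4.1, 5.5, 9.2 and 9.4.1 all say that the pilot is not sized to show efficacy.

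**The concern.** The table is indexed on the intervention arm, but the only rate the paragraph states is for eligible children in general, which is the natural anchor for usual care. Multiplying the column rates by 3 to 5 moves the control arm away from that anchor in most cells. The printed powers also look low for six months of follow-up with these rates and effects.

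The pilot's size does not depend on the table, so the decision to run it is not at stake. What is at stake is the message on precision. Sections 4.2 and 9.4.3 say the pilot will give effect sizes precise enough to size the next trial. A reader planning that trial would take 19-88% as the attainable power. The range describes neither the rate the plan states nor a correct calculation for the rates it tabulates.

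**Working it through.** **Inputs.** From Section 9.2: two-sided 0.05; overdispersion φ = 1; 45 per arm with up to 10% missing, so n = 40 to 40.5 evaluable; λ = 0.02, 0.04, 0.06, 0.08, 0.10 per patient-month; RR = 3, 4, 5. I read the printed 0.40 as 0.04, since 10 / (40.5 × 6) = 0.041. From Section 6.3: allocation 1:1. From Section 9.4.3: six months of follow-up.

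**Step 1: implied control rates.** Control rate per year = 12 × λ × RR.

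| RR | λ 0.02 | 0.04 | 0.06 | 0.08 | 0.10 |
|---|---|---|---|---|---|
| 3 | 0.72 | 1.44 | 2.16 | 2.88 | 3.60 |
| 4 | 0.96 | 1.92 | 2.88 | 3.84 | 4.80 |
| 5 | 1.20 | 2.40 | 3.60 | 4.80 | 6.00 |

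Only the first column brackets 1 per year; the other 12 cells need 1.44 to 6.0.

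The 50% estimate allows a higher rate if it means severe illness over six months. With φ = 1, 1/(1 + μ) = 0.5 gives μ = 1, or 2 per year. Under a Poisson model, μ = ln 2 = 0.693, or about 1.4 per year. Even against 2 per year, 10 of 15 cells are higher.

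**Step 2: reproducing the printed powers.** Let μ = λ × months of exposure, with subscripts I for intervention and C for control.
- V1 = (1/μ_I + 1/μ_C + 2φ)/n
- V0 = (4/(μ_I + μ_C) + 2φ)/n (pooled null)
- Power = Φ[(ln RR − 1.96√V0)/√V1]; the unpooled form uses V1 in both places.

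No variant tried with six months of exposure gave the printed values. With **one** month, pooled null and n = 40, the lowest cell has μ_I = 0.02 and μ_C = 0.06, so √V1 = 1.310 and √V0 = 1.140. Then (1.099 − 1.96 × 1.140)/1.310 = −0.867, which is 19.3%.

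| RR | Printed | Computed, 1 month | Computed, 6 months |
|---|---|---|---|
| 3 | 19, 29, 38, 45 | 19, 29, 38, 45 | 57, 78, 87, 91 |
| 4 | 31, 41, 59, 68 | 31, 47, 59, 68 | 80, 94, 98, 99 |
| 5 | 42, 62, 74, 83 | 43, 62, 74, 83 | 92, 99, >99, >99 |

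The columns are λ = 0.02 to 0.08, in %. At one month, RR 5 with λ = 0.10 gives 88%, the top of the stated range; Step 1 puts that corner at a control rate of 6 per year. Eleven of the 12 legible cells agree within one point. The exception is RR 4 at 10 illnesses, printed 41% and computed 47%.

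For the lowest cell at **six** months, μ_I = 0.12 and μ_C = 0.36, so √V1 = 0.573 and √V0 = 0.508. Then (1.099 − 0.996)/0.573 = 0.179, which is 57%. The unpooled form gives 48%.

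**Step 3: power at the stated rate.** A 40% reduction is RR = 1/0.60 = 1.67. With control 1 per year (μ_C = 0.5), six months, n = 40.5 and φ = 1:

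| RR | Unpooled | Pooled |
|---|---|---|
| 1.67 | 22% | 24% |
| 2 | 34% | 38% |
| 3 | 60% | 68% |
| 4 | 72% | 82% |
| 5 | 78% | 88% |

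At RR 1.67, μ_I = 0.3 and √V1 = √((3.33 + 2 + 2)/40.5) = 0.426. The 95% limits are the estimate divided and multiplied by exp(1.96 × 0.426) = 2.3, so an estimate of 1.67 would carry limits of about 0.72 to 3.84.

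Sensitivity at RR 1.67: 15-28% (unpooled) for control rates of 0.5 to 1.5 per year; 32-34% (unpooled to pooled) at 2 per year; 19-25% (unpooled) for φ from 2 to 0.5.

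**The case against.** The strongest reply is that this is a pilot whose primary outcomes are feasibility, acceptability and fidelity. The plan says repeatedly that it is not powered for efficacy, labels these effects as large, and offers the table as a grid of scenarios. All of that stands, and it limits the consequence. It does not make the printed values right for their own inputs, nor does it explain why the grid omits smaller effects.

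Three stronger readings are tempting, and the documents do not support them.
- **That the plan rules out the tabulated rates and effects.** It gives an average from preliminary work and excludes nothing. Its 50% estimate could be read as implying 1.4 to 2 per year, which would also accommodate the 1.44 and 1.92 cells.
- **That 88% power cannot be reached at one illness per year.** This depends on the variance form. The unpooled test gives 78% at RR 5 and 85% at RR 10. The pooled form, which matches the printed table, gives 88% at RR 5, and a simulated likelihood-ratio test with 40 per arm gives 87%.
- **That 1.67 is the effect assumed for RE-PACT.** It comes from a different outcome and a broader population, and the intervention has since been adapted. It is a benchmark, though the only one the documents offer.

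**Conclusion.** The point holds as two inconsistencies within Section 9.2. The grid departs from the stated average of one severe illness per year in 12 of 15 cells and shows no effect below RR 3. The printed powers do not follow from six months of follow-up.

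The two faults pull in different directions. Correcting exposure alone raises every legible cell, to between about 48-57% and over 99%, but mostly at control rates above the stated average. Anchoring on one illness per year and including RR 1.67 brings the figure for that benchmark to about 22-24%. It would therefore be wrong to infer simply that the plan overstates its power: for its own inputs it understates it.

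These figures rest on a Wald test for two negative binomial rates, φ = 1, 40 to 40.5 evaluable per arm with six months each, and the reading of 0.40 as 0.04. That a one-month exposure caused the discrepancy is inferred from the match; the protocol does not say so.

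**What to change.** Replace the table and its closing sentence.
- Recompute with six months of exposure and name the variance method.
- Index the table on the control arm: 1 severe illness per child-year, with sensitivity at 0.5, 1.5 and 2; RR 1.5, 1.67, 2, 3, 4 and 5; about 40 evaluable per arm; φ = 0.5, 1 and 2.
- Add the expected 95% confidence-interval width for each scenario, since estimation is the stated aim.
- If any of the present table is kept, correct 0.40 to 0.04 and check the 41% cell.
- In place of the 19-88% sentence, give the range at one illness per year: about 22-24% at RR 1.67, 34-38% at RR 2, 60-68% at RR 3 and 78-88% at RR 5 (unpooled to pooled, 40.5 per arm, φ = 1), with limits at RR 1.67 of the estimate divided and multiplied by about 2.3. Describe 1.67 as a benchmark from the PACT trial.
- State whether the 50% estimate refers to severe illness. If it does, reconcile it with one per year: a six-month mean of 0.5 gives only 33% (φ = 1) or 39% (Poisson) with at least one event.

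The cost is one table and a sentence or two. The sample size and the statement that the pilot is not powered for efficacy stay as they are.

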4.2 SCIENTIFIC RATIONALE FOR STUDY DESIGN

Rational for the study design. Conducting this pilot study will provide a high degree of certainty that the final RE-PACT protocol is feasible, acceptable and can be delivered with fidelity. This is a critical approach to designing interventions that can be integrated in diverse, real-world, settings and sustained.

Using an RCT design (i.e., with a control group who do not receive intervention) is necessary to establish effect sizes needed to adequately power an efficacy trial. The findings from this study will allow precise estimation of effect sizes to conduct a fully powered, multisite hybrid Type 2 effectiveness-implementation RCT.

Rationale for the type and selection of control conditions. The control group will be randomly assigned, allowing the study team to conclude that endpoint differences between each group are most likely due to the intervention itself.

Potential problems associated with the control group. The control group may have pre-existing respiratory action plans created during routine clinical care. In addition, the coach may have difficulty avoiding contaminating the control group by inadvertently conducting coaching activities to those not assigned to the intervention group. This risk will be minimized since action plans using the study protocol will only happen for intervention subjects, and coaching is triggered only through mHealth text responses and texting will only be set up for those assigned to the intervention.

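### The power table in Section 9.2 does not follow from its stated 6-month follow-up: the printed powers match one month of exposure per child, so the 19-88% range is wrong as written

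*Combined protocol and SAP*

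**What the plan says.** Section 9.2 gives a table of attainable power for the primary clinical outcome, from a negative binomial (NB) regression with overdispersion 1.0, "assuming a sample size of 45 subjects per arm with a missing value rate of 10% or less". The columns are headed "Number of severe respiratory illnesses in intervention arm over 6-month Follow-up period" and run 5, 10, 15, 20, 25. Under each count stands a rate λ, footnoted as "Severe respiratory illness rate per patient-month". The rows are control-to-intervention rate ratios (RR) of 3, 4 and 5. The closing sentence says that such effects "will be detected with 19-88% power at the two-sided 0.05 significance level".

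The same section gives the planning rate: "eligible children average one severe respiratory illness per year and we estimate 50% of participants will experience at least one respiratory illness". Section 9.4.3 defines the outcome as "the total number of severe respiratory illnesses divided by the person-months over the 6-month follow-up period", and Section 9.1 does the same. On what the estimates are for, Section 4.2 says "The findings from this study will allow precise estimation of effect sizes to conduct a fully powered", and Section 9.4.3 says that they will "allow precise sample size calculations for a future large-scale trial".

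**The concern.** The power for a count outcome depends on the mean count per child, which is the monthly rate times the months observed. The column heads use six months. The printed powers look too low for that: a threefold ratio with about 5 against 15 events is given only 19%.

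This table is the plan's only quantitative statement of what the clinical comparison can detect. If its powers belong to a different exposure, they do not describe this trial. The scenarios also need a check against the expected illness rate, because a table corrected for exposure alone would show high power in most cells, beside a text that says the sample is not powered for efficacy.

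**Working it through.** **Inputs (Section 9.2 unless noted).** Two-sided α = 0.05; φ = 1; 45 per arm less 10% = 40.5, taken as n = 40; λ = 0.02, 0.04, 0.06, 0.08, 0.10 per patient-month; RR = 3, 4, 5; exposure t = 6 months (also Sections 9.1 and 9.4.3). The second λ reads 0.40 in the text available to me. I used 0.04, which fits its neighbours and its column head of 10. Four power values per row are legible. The fifth column is known only through the 88% in the sentence.

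**Step 1: which exposure links the counts to the rates?** Illnesses = λ × t × 40.5.
- Six months: 0.02 × 6 × 40.5 = 4.9, up to 0.10 × 6 × 40.5 = 24.3. This matches 5 to 25.
- One month with n = 40: 0.8 to 4.0. This does not match.

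**Step 2: reproduce the printed powers.** Let m_I = λt, m_C = RR × λt, and m̄ be their mean.
- SE₁ = √[(1/m_I + 1/m_C + 2φ)/n]; SE₀ = √[(2/m̄ + 2φ)/n]
- Pooled null: power = Φ[(ln RR − 1.96·SE₀)/SE₁]
- Wald: power = Φ[ln RR/SE₁ − 1.96]

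The plan does not name its formula. The pooled form with t = 1 fits:

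| RR | Printed (%) | Pooled, t = 1, n = 40 (%) |
|---|---|---|
| 3 | 19 / 29 / 38 / 45 | 19.3 / 29.3 / 37.9 / 45.3 / 51.6 |
| 4 | 31 / 41 / 59 / 68 | 31.2 / 47.1 / 59.0 / 68.1 / 75.0 |
| 5 | 42 / 62 / 74 / 83; top of range 88 | 42.6 / 61.9 / 74.4 / 82.7 / 88.1 |

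Eleven of 12 legible cells and the 88% bound agree within 1 point. The exception is 41%, against 47%. Wald at one month (13.1 to 77.7) and pooled with n = 45 (20.7 to 91.0) do not fit.

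**Step 3: the same formulas with t = 6.** First cell: m_I = 0.12, m_C = 0.36, m̄ = 0.24. SE₁ = √[(8.33 + 2.78 + 2)/40] = 0.573 and SE₀ = √[(8.33 + 2)/40] = 0.508. Pooled: Φ[(1.099 − 0.996)/0.573] = 57%. Wald: Φ[1.099/0.573 − 1.96] = 48%. The printed value is 19%.

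| RR | Pooled, t = 6 (%) | Wald, t = 6 (%) |
|---|---|---|
| 3 | 57 / 78 / 87 / 91 / 94 | 48 / 71 / 83 / 89 / 92 |
| 4 | 80 / 94 / 98 / 99 / 99 | 70 / 90 / 96 / 98 / 99 |
| 5 | 92 / 99 / >99 / >99 / >99 | 84 / 97 / 99 / >99 / >99 |

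No legible cell reproduces. Leaving the 41% cell aside, the printed values are 17 to 50 points too low (pooled) or 17 to 45 (Wald). Simulated NB regression on arm and site (800 replicates per cell; Wald and likelihood-ratio tests) gave 48-52% at RR 3 with 5 illnesses, 85% at RR 3 with 15, and over 99% at RR 5 with 25.

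**Step 4: other readings of φ, at six months.** If φ = 1 applies to each month (1/6 over six months), the lowest cell is 54% (Wald) or 64% (pooled). If the variance is linear, at twice the mean, it is 31% or 41%. Neither gives 19%.

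**Step 5: the scenarios against the planning rate.** Control rate per child-year = RR × λ × 12:
- RR 3: 0.72 / 1.44 / 2.16 / 2.88 / 3.6
- RR 4: 0.96 / 1.92 / 2.88 / 3.84 / 4.8
- RR 5: 1.2 / 2.4 / 3.6 / 4.8 / 6.0

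Against one per year, 12 of 15 cells are at least 44% higher. The 50% statement does not say severe illness. If it means that, φ = 1 gives P(≥1) = m/(1 + m) = 0.5, so m = 1 per six months, or 2 per year, and 10 of 15 cells still exceed it.

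**Step 6: power at the planning rate** (t = 6, n = 40, φ = 1; Wald to pooled, %).

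| Control rate | RR 1.5 | RR 2 | RR 3 | RR 4 | RR 5 |
|---|---|---|---|---|---|
| 1 per year (m_C = 0.5) | 16-17 | 34-37 | 59-67 | 72-81 | 78-88 |
| 2 per year (m_C = 1.0) | 23 | 50-53 | 81-85 | 91-95 | 95-98 |

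The expected 95% interval factor is exp(1.96 × SE₁). At one per year it is 2.27 for RR 1.5 (0.66 to 3.4) and 2.40 for RR 2 (0.83 to 4.8).

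**The case against.** The strongest case is about weight. The primary endpoints are descriptive, n = 90 rests on feasibility, and the plan says repeatedly that it is underpowered for efficacy. The later trial will be sized from observed estimates, not from this table, and the error understates power. All of that stands, and it limits the point to a correction of a stated figure.

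Second, the replacement values are less certain than a single row suggests. The formula is unstated, and the pooled form runs above the simulation in the sparsest cells (57% against 48-52%; at RR 4 with 5 illnesses, 80% against 74-76%). This stands too: corrected powers should be read as a range across formulas, and one month of exposure is an inference from the fit. The mismatch itself does not depend on that inference, because every variant tried at six months with the stated n and φ puts the lowest cell at 31% or more.

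Third, the table is damaged in the text available. The λ of 0.40 and the 41% cell may be reading errors and are not counted as mistakes in the plan. The 19-88% sentence is intact.

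Last, the choice of scenarios and the word 'precise' are separate from the exposure error. That is fair. Correcting the exposure changes no confidence interval, and the extra rows are an addition to the correction.

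**Conclusion.** The concern holds. The stated 19-88% does not follow from the stated design. With 6-month means, 40 per arm and φ = 1, the range is about 57% to over 99% (pooled) or 48% to over 99% (Wald). The likely cause is that the monthly rate was entered as the mean count per child.

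Correcting the exposure alone would put 12 (Wald) or 13 (pooled) of 15 cells at or above 80%; the thirteenth is the 80.3% cell that simulation puts below 80%. Such a table would sit oddly beside the statement that the sample is not powered. The statement itself remains sound for smaller effects at the plan's own rate: 16-37% for RR 1.5 to 2 at one illness per child-year. An interval factor of 2.3 to 2.4 either way also shows that 'precise' claims too much.

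The result assumes NB variance m + φm² on the 6-month count and λ = 0.04 in the second column. It should be fixed, but it does not threaten the design.

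**What to change.** In Section 9.2:
- Recompute the table with mean count = λ × 6 months. State the variance formula, the n per arm after 10% missing data, and whether φ applies to the 6-month count.
- Replace the 19-88% sentence with the recomputed range.
- Check the second λ heading and the 41% cell against the original page.
- Add rows at a control mean of 0.5 per six months, and at 1.0 if the 50% statement means severe illness. Include RRs below 3 and the expected confidence interval width.

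In Sections 4.2 and 9.4.3, soften 'precise' to match that width.

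The cost is one recalculation and a few lines of text. Enrolment, conduct and the planned analysis do not change.
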